### 15.1. Statistical Analysis Plan

Details regarding the final data analysis will be discussed in a separate Statistical Analysis Plan (SAP). The study data from Part 1 and Part 2 of the trial will be analyzed separately.

### 15.2. Determination of Sample Size

#### Part 1

There is no formal sample size calculation for Part 1 (dose escalation and expansion).

#### Part 2

The primary analysis of efficacy will be performed when at least 82 PFS events have been observed and documented. If the median time to PFS is assumed to be 5 months in the placebo plus axitinib control group, then a total of 82 PFS events will provide approximately 80% power to detect a 3 month extension from 5 to 8 months in the dalantercept plus axitinib experimental treatment group when performing a stratified log-rank test of the null hypothesis of no difference between treatment groups using a one-sided 10% significance level.

The projection of power is made under a proportional hazards assumption so that the hazard ratio (HR) for dalantercept plus axitinib relative to placebo plus axitinib is equal to 0.625 under the alternative hypothesis. It is projected that 130 patients will need to be randomized to obtain 82 PFS events. The number of patients to be randomized provides for patient censoring patterns that could occur under the alternative hypothesis in the event the dropout rate is higher than expected in either treatment group.

### **15.3. Part 1 – Safety and Tolerability Analyses**

The assessment of safety will be based mainly on the frequency of adverse events (overall, related, and SAE) and on the frequency of clinically meaningful abnormal laboratory values. Other safety data (e.g., vital signs, ECHO, ECG) will be summarized as changes from baseline and frequency counts as appropriate. All safety data will be listed. The primary study population will be the AT population.

PFS, OS, ORR, duration of response, disease control rate, and PD biomarker studies will be analyzed in a similar manner as described in Part 2.

### **15.4. Part 2 – Efficacy and Safety**

#### **15.4.1. Primary Endpoint**

**Progression free survival:** PFS is the primary endpoint in Part 2 and will be defined as the date of radiographic (also called documented) tumor progression (per RECISTv1.1) or death from any cause, whichever is earliest, minus date of randomization (or first date of dosing in Part 1 as will be implied throughout) plus one day. The term “on-study” will refer to the period from randomization until 28 days after last dose of study medication. Patients will be censored (i.e., those patients not exhibiting radiographic tumor progression or death) on the date of the last tumor assessment on-study and includes:

- Those patients discontinuing study medication due to any reason and having at least 1 radiographic tumor assessment before or on the date of discontinuation
- Those patients in whom radiographic tumor progression or death occurs following  $\geq 2$  consecutive scheduled missing radiographic tumor assessments
- Those patients given non-study antitumor medication or treatment prior to documentation of radiographic tumor progression

Patients missing baseline radiographic tumor assessments will be censored on the date of randomization. Patients with missing post-randomization radiographic tumor assessments will be censored on the date of randomization unless death occurred prior to the first and second scheduled radiographic tumor assessment, whereby death is the event.

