### **12.2. Dosing Days and Interim Visits**

- All screening and study day 1 procedure results required to confirm eligibility must be obtained and reviewed prior to study drug administration. Patient eligibility for inclusion/exclusion criteria must be confirmed from these results, as applicable. Ideally, patients should be randomized within 48 hours of C1D1.
- Baseline hematology, chemistry, and urinalysis results must be reviewed prior to dosing on C1D1 but may be collected up to 72 hours prior to dosing. Baseline thyroid function may also be collected up to 72 hours prior to dosing. Therefore if the screening visit occurs within 72 hours of study day 1, the hematology, chemistry, thyroid function and urinalysis testing do not need to be repeated.
- Any non-serious AEs that occur prior to dosing in cycle 1 should be recorded in the medical history section of the CRF.
- All AEs that occur after dosing in cycle 1 should be recorded in the AE page of the CRF.

- On subsequent dosing days, all AEs and abnormal laboratory or other findings that might require modification of dosing (see [Section 10.6](#)) should be reviewed prior to dosing to ensure that the patient is still eligible to receive additional doses of dalantercept/placebo. Please note that there is an extended window of up to 5 days for the ECHO and tumor response assessment scan, when required.
- PK blood sample collection should be performed pre-dose for dalantercept/placebo and axitinib at C1D1, C2D1 and C3D1.
- Tumor response assessment scans should be performed every 6 weeks regardless of dalantercept/placebo or axitinib dosing delays through C15. After C15 tumor response assessment scans should be performed every 12 weeks regardless of dalantercept/placebo or axitinib dosing delays (e.g. C19D1, C23D1, etc.).
- The schedule of events outlines procedures through C6D1. If patients have stable or responding disease and are able to continue beyond 6 cycles of treatment, the procedures outlined for cycle 5 and 6 should be repeated until the patient comes off study (i.e. C7D1=C5D1, C8D1=C6D1, etc.). The only exception is that after cycle 5, ADA, urinalysis, thyroid function and PD biomarkers are required once every 4 cycles instead of once every 2 cycles (i.e., C9D1, C13D1, etc.).

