#### **Missing Radiological Assessments and Non-evaluable (NE) Designation**

If all lesions cannot be evaluated due to missing data or poor image quality the patient is not evaluable (NE) at that time point. If only a subset of lesions can be evaluated at an assessment, the visit is also considered NE.

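### Section 15.4.1 sets one PFS censoring date for all listed groups, so an on-treatment patient who progresses after a scan gap can be censored on the progression scan itself

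*Combined protocol and SAP*

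**What the plan says.** Section 15.4.1 defines PFS from randomization to radiographic progression or death. It describes censored patients as "those patients not exhibiting radiographic tumor progression or death" and censors them "on the date of the last tumor assessment on-study and includes" three groups:

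- patients who stop study medication for any reason and have at least one radiographic assessment by then;
- "Those patients in whom radiographic tumor progression or death occurs following" two or more "consecutive scheduled missing radiographic tumor assessments";
- "Those patients given non-study antitumor medication or treatment prior to documentation of radiographic tumor progression".

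The term on-study "will refer to the period from randomization until 28 days after last dose of study medication". No separate date is given for the second or third group.

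The subsection on missing radiological assessments adds: "If only a subset of lesions can be evaluated at an assessment, the visit is also considered NE". The censoring sentence does not require the assessment that sets the date to be evaluable.

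Section 12.2 fixes the scan interval: "Tumor response assessment scans should be performed every 6 weeks regardless of dalantercept/placebo or axitinib dosing delays through C15". After C15 it is 12 weeks. Sections 15.3 and 15.4.2 carry a similar PFS analysis to Part 1 and to the subgroup with two or more prior lines.

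**The concern.** A scan-gap rule exists because the time of progression is unknown when scans are missing. Having declined to count the late progression as an event, the analysis should end follow-up when the patient was last known to be progression-free. The stated date does not ensure this. If the patient is still on study drug when the late scan is done, that scan is the last on-study assessment. The patient then stays in the risk set through the whole unassessed interval and leaves it as a censored observation on the day progression was seen.

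The sentence also contradicts itself: its parenthesis limits censoring to patients without progression or death, while the second bullet lists patients who had one or the other. Two programmers could derive different dates for the primary endpoint, and each could cite the text.

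A scan taken after other antitumor treatment began, or one that could not be evaluated, can set the date in the same way.

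**Working it through.** **Plan's own figure.** Inputs from Section 15.2: hazard ratio 0.625 (5/8), one-sided alpha 0.10, power 80%, 1:1 allocation. Schoenfeld formula: events = 4(z₀.₉₀ + z₀.₈₀)² / (ln 0.625)² = 4 × 2.1232² / 0.4700² = 81.6, so 82. Power at 82 events is 80.1%. The plan reproduces. Moving a censoring date does not change it, because the affected patients are censored under either rule.

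**Length of the interval.** Suppose the last clean scan is on schedule, the next two are missed, and progression is seen at the third.

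- 6-weekly phase: 3 × 42 = 126 days; 126 / 30.4375 = 4.1 months, against an assumed control median of 5 months.
- 12-weekly phase: 3 × 84 = 252 days; 252 / 30.4375 = 8.3 months.

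Longer gaps add more.

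**Which patients are affected.**

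| Situation | Literal censoring date |
|---|---|
| Gap, then progression scan while on drug or within 28 days of last dose | The progression scan |
| Gap, then death with no further scan | Last scan before the gap (no problem) |
| Gap, then progression scan more than 28 days after last dose | Last scan before the gap (no problem) |
| New systemic treatment, final-visit scan on days 20 to 28 | That scan, after the new treatment began |
| Last on-study scan non-evaluable | The non-evaluable scan |

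The days 20 to 28 come from the final-visit window of 30 ± 10 days (Schedule of Events, footnote 17; Section 12.2.1) and the 28-day on-study limit. They assume that the last dose of study medication is the last dalantercept/placebo dose.

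**Effect on the hazard ratio, no true difference.** Assumptions, none of them from the documents except the median and scan schedule: exponential PFS with median 5 months in both arms, scans at weeks 6 to 42 and then every 12 weeks, follow-up uniform from 20 to 91 weeks, and a stated share of patients missing the two scans before the one that detects progression.

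| Gap rate, dalantercept / placebo | HR as written | HR, pre-gap date | Shift due to the date |
|---|---|---|---|
| 8% / 2% | 0.906 | 0.934 | 0.028 |
| 2% / 8% | 1.091 | 1.057 | 0.034 |
| equal | about 1.00 | about 1.00 | about 0 |

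Most of the departure from 1 remains after the date is corrected: at 8% / 2% it is 0.066 (1 − 0.934) of 0.094 (1 − 0.906). That part comes from censoring scan-gap patients at all.

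**Effect under the planned alternative.** Medians 8 and 5 months, 18-month cut-off, 20,000 simulated patients per arm; HR without gaps 0.615. Here the rate is the share of patients with a two-scan gap starting at one of the first four scans. Only some of these gaps affect the outcome (about 3% of patients at a 10% rate).

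| Gap rate, dalantercept / placebo | HR as written | HR, pre-gap date | Difference |
|---|---|---|---|
| 10% / 10% | 0.617 | 0.612 | 0.005 |
| 20% / 20% | 0.621 | 0.612 | 0.009 |
| 30% / 30% | 0.623 | 0.610 | 0.013 |
| 30% / 10% | 0.566 | 0.575 | 0.009 |
| 10% / 30% | 0.679 | 0.649 | 0.030 |

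With unequal rates the written rule favours the arm with more gaps, whichever that is. With equal rates the shift is small and slightly against dalantercept.

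**The case against.** Several points on the other side are sound.

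- **Known progression.** A reader might infer that time after known progression is credited as progression-free. The documents do not support that. Follow-up ends at the progression scan, treatment stops at progression (Section 9.1), and the final-visit scan is not repeated once progression is confirmed. The credited time is unassessed time before the scan.
- **Direction.** A reader might infer that dalantercept's hold and discontinuation rules tilt the result towards dalantercept. Scans run regardless of dosing delays, a delay beyond 3 weeks generally ends participation (Section 10.6.1), and the on-study window closes 28 days after the last dose. The documents give no reason to expect more gaps in one arm.
- **Frequency.** The scan-gap case needs a patient dosed through about 18 weeks without scans, although Section 11.4.1 asks for absence of progression to be established before each cycle. The 36-week case arises only after C15.
- **New therapy.** Other anticancer treatment leads to discontinuation (Section 10.2), and 3-monthly scans are then not required (Section 12.2.2). The route is narrow for systemic treatment. It widens if the palliative radiation permitted in Section 10.6.1 counts as non-study treatment, because those patients stay on drug and keep being scanned; Section 15.4.1 does not say.
- **The parenthesis.** It can be read as pointing to a progression-free assessment. It then conflicts with the scan-gap bullet, so it does not settle the date.
- **Deferral.** Sections 15.1 and 15.6 leave detail to a separate SAP. Section 15.4.1 nevertheless states a date, and nothing in the text reviewed corrects it. The one sensitivity analysis described counts patients going off-study for symptomatic progression, change of treatment or declining performance status as events; it does not address scan gaps.

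These points limit the size and remove any presumed direction. They do not make the stated date right.

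**Conclusion.** The point holds as a defect in the primary-endpoint definition that should be corrected. The single date contradicts the purpose of the scan-gap rule, and the sentence that sets it is internally inconsistent. For an affected patient the excess is at least 126 days when progression is found at a scheduled scan, and 252 days in the 12-weekly phase.

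At trial level the effect is modest: about 0.03 on the hazard ratio under assumed gap rates of 8% and 2%, in either direction, and about 0.00 to 0.01 with equal rates. These rates are illustrations, since the documents give none. It would be wrong to attribute the whole departure from 1 in the no-difference simulation to the date, because about two-thirds of it remains after the correction. The event target and power stand. The new-therapy and non-evaluable routes follow from the wording but were not quantified.

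**What to change.** In Section 15.4.1 and the SAP, replace the single date as follows. Censor at the last evaluable tumor assessment without progression that falls (i) before the first of the consecutive missed assessments, for scan-gap patients; or (ii) on or before the start of non-study antitumor treatment, for new-therapy patients. For all others, use the last evaluable on-study assessment without progression.

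Reword the parenthesis so that it agrees with the scan-gap bullet. State whether the palliative radiation permitted in Section 10.6.1 counts as non-study antitumor treatment for this analysis. Use the same dates in every sensitivity analysis that keeps these censoring groups, and in the Part 1 and subgroup analyses.

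The cost is a short text change and a small programming change before database lock, with no new data and no change to the event target. The downside is slightly shorter follow-up for some censored patients.

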### **10.3. Randomization and Blinding**

**Part 1:** This is an open-label dose escalation that does not require randomization.

**Part 2:** Patients will be randomized to receive 0.9 mg/kg of dalantercept or placebo plus axitinib 5 mg PO BID. Randomization assignments will be generated through a computerized system, provided by an Interactive Web Response System (IWRS). Patients who have signed informed consent and met all eligibility criteria will be stratified according to prior mTOR therapy and prior immune therapies. Patients will then be randomly assigned to dalantercept or placebo plus axitinib within each stratum.

Only the pharmacist or his/her designee who prepares the study drug (dalantercept or placebo) and an unblinded clinical research associate at the CRO will be unblinded to the patient treatment assignments. All other study personnel, including but not limited to Investigators, study coordinators, nursing staff, clinical monitors, the Sponsor, and the Sponsor's representatives, will remain blinded to the study treatment assignments.

In the event of a medical emergency for an individual patient in which knowledge of the study drug is critical to the patient's medical management, the investigator may break the blind for that patient. However, prior to breaking the blind, every effort must be made by the investigator to first discuss the need to break the blind with the medical monitor. Further, it must be determined by the investigator that breaking the treatment blind is necessary information for the medical management of that patient. If the blind is broken, investigator discretion, in consultation with the medical monitor as needed, should be used to determine if the patient should continue on treatment or be discontinued from the study.

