### **Part 2**

A data monitoring committee (DMC), independent from the sponsor, will be established to review unblinded safety data on a regular basis and to make appropriate recommendations regarding the conduct of the trial.

The first DMC safety review will occur when 25 patients are randomized. Thereafter, DMC review meetings will be performed at approximately 6 month intervals until the end of the study. If agreed by the DMC and Acceleron, this schedule may be modified based on the rate of patient accrual and findings from DMC reviews. A detailed charter will outline all activities of the DMC (including, but not limited to, type of data to be reviewed, DMC responsibilities, communication paths, and frequency of meetings).

The unblinded safety analyses will be generated for the DMC by an independent statistician.

In order to evaluate study assumptions for the primary endpoint of PFS, a blinded sample size re-estimation (BSSR) will be performed after 85 patients have been recruited. Based on the

results of the BSSR, the DMC will recommend either to continue enrollment to the original planned sample size (n=130) or to increase the sample size to a specified number. The BSSR will be performed from the pooled treatment group survival data. Details will be provided in the Statistical Analysis Plan and the DMC charter. Since the treatments will remain blinded and no inference will be performed during this analysis, the type I error rate for the final analysis will be preserved. Enrollment will continue during the BSSR.

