## 15. STATISTICS

### Statistical Methods:

#### Study Design Overview

A dose escalation plus expansion cohort design to evaluate the safety of dalantercept plus axitinib will be implemented to determine the recommended Phase 2 dose level of dalantercept for Part 2 of the trial.

Part 2 is a randomized placebo-controlled trial in previously treated advanced RCC patients. The randomization will be stratified by prior mTOR therapy and prior immune therapy. The primary endpoint for statistical analysis is PFS defined as the time from randomization to documented progression or death based on the investigator assessment.

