## 15.6. Deviation from Original Analysis Plan

A formal SAP for the analysis and presentation of data from this study will be prepared before database lock. Deviations from the statistical analyses outlined in this protocol will be indicated in this plan; any further modifications will be noted in the final clinical study report.

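### As most naturally read, the primary PFS rule in Section 15.4.1 counts progression or death after treatment stops but deletes event-free follow-up over the same period

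*Combined protocol and SAP*

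**What the plan says.** **Event.** Section 15.4.1 counts radiographic progression or death from any cause, whichever comes first, with no time limit. The Study Design Overview in Section 15 likewise gives "PFS defined as the time from randomization to documented progression or death based on the investigator assessment".

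**Who is censored.** The lead-in in Section 15.4.1 restricts censoring to "those patients not exhibiting radiographic tumor progression or death". Three bullets follow:
- Bullet 1: "Those patients discontinuing study medication due to any reason and having at least 1 radiographic tumor assessment before or on the date of discontinuation".
- Bullet 2: "Those patients in whom radiographic tumor progression or death occurs following" two or more consecutive missed scheduled scans. These patients do have an event.
- Bullet 3: patients given other antitumor treatment before documented progression.

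**Censoring date.** It is the last on-study tumor assessment, where on-study means "the period from randomization until 28 days after last dose of study medication".

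**Follow-up.** Section 9.1 sends Part 2 patients into follow-up for progression and survival after the final visit. Section 12.2.2 and footnote 19 of the Schedule of Events ask unprogressed patients to return about every 3 months for scans. Patients who start a new therapy or continue axitinib alone are exempt. Footnote 17 puts the final visit about 30 days, plus or minus 10, after the last dalantercept/placebo dose.

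**Timing.** Under Section 10.7, "a blinded sample size re-estimation (BSSR) will be performed after 85 patients have been recruited". Section 15.2 triggers the primary analysis at 82 or more events. Section 15.6 says "A formal SAP for the analysis and presentation of data from this study will be prepared before database lock".

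**The concern.** An event and the time at risk for that event should come from the same follow-up. Here they need not. Take two patients who stop without progression and are both scanned four months later. One has progressed and supplies an event at that date. The other is clean and is cut back to a scan no later than 28 days after the last dose. The numerator of the hazard after stopping keeps the late failures, and the denominator loses the late event-free time.

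If both arms stop equally, the distortion largely cancels. If one arm stops more, that arm's hazard is inflated more, so the log-rank test and the hazard ratio move for a reason unrelated to treatment effect.

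The wording also leaves some room for a second reading. Bullet 1 covers stopping for any reason and does not add that no later event occurred. Bullet 2 shows that the list can reach patients who have events. On that reading all stoppers are censored at the window. The 82-event count, the primary test and the pooled data for the sample size re-estimation all depend on which rule applies.

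**Working it through.** **1. The plan's own figure.** Inputs from Section 15.2: HR 0.625, one-sided alpha 0.10, power 0.80, and 1:1 allocation (Section 9.1).

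Events = 4(1.2816 + 0.8416)² / (ln 0.625)² = 4 × 4.508 / 0.2209 = 81.6, so 82.

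Power at 82 events = Φ(√82/2 × 0.470 − 1.2816) = 0.801.

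The sample-size arithmetic is right. The issue is which data supply the events and the time at risk.

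**2. Three rules compared.**
- *Mixed* (the natural reading): late events count; event-free stoppers are censored at the last scan in the 28-day window.
- *All follow-up*: late events count; event-free patients are censored at their last evaluable scan, on or off treatment.
- *Window only*: neither late events nor late event-free time counts.

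**3. The mechanism by hand.** Take stoppers with the control hazard, λ = ln 2 / 5 = 0.1386 per month, followed for 6 months (two 3-monthly scans), ignoring scan spacing.
- Probability of an event = 1 − exp(−0.8318) = 0.565.
- Expected time at risk per patient = 0.565 / 0.1386 = 4.07 months.
- Of this, event-free patients supply 0.435 × 6 = 2.61 months, which the mixed rule deletes, leaving 1.46.
- Apparent hazard = 0.565 / 1.46 = 0.386, which is 2.8 times the true value among followed stoppers.

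The effect on the whole-trial HR is much smaller, because only some patients stop without progression and some of those are not scanned.

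**4. Effect on the hazard ratio (large-sample simulation).** The documents give no stopping rates or accrual period. Assumed: 18 months' accrual plus 6 months' follow-up; stopping without progression by month 5 of 10% (control) and 30% (dalantercept); 25%, 50% or 100% of stoppers still scanned.

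| Rule | HR, medians 5 vs 8 | HR, medians 5 vs 5 |
|---|---|---|
| Mixed | 0.675, 0.696, 0.731 | 1.028, 1.040, 1.067 |
| Window only | 0.650, 0.649, 0.649 | 1.004, 0.998, 0.999 |
| All follow-up | 0.650, 0.648, 0.644 | 1.005, 0.999, 0.995 |

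With 20% stopping in each arm, the three rules differ by at most about 0.02.

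**5. Type I error (one-sided, nominal 0.10).** Assumed: 65 per arm, both medians 5 months, 18-month accrual, hazard after stopping equal to control, 0% or 50% of stoppers exempt from scans, stratified log-rank, 9,000 trials per case (Monte Carlo SE about 0.003).

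| Stopping, dalantercept / placebo | Mixed | Window only |
|---|---|---|
| 30% / 12% | 0.062–0.065 | 0.077 |
| 20% / 8% | 0.076 | 0.086 |
| 15% / 15% | 0.097–0.099 | 0.097 |
| 8% / 20% | 0.126 | 0.111 |
| 12% / 30% | 0.144–0.145 | 0.118 |

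All follow-up gave 0.091–0.108 across these cases.

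A simpler simulation with every stopper scanned and an unstratified test (1,200 trials per case, SE about 0.01) gave, for mixed, window only and all follow-up:
- 30% / 12%: 0.052, 0.083, 0.105
- 12% / 30%: 0.166, 0.115, 0.102
- 15% / 15%: 0.124, 0.118, 0.119

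A further rough simulation gave the mixed rule about 0.08 when dalantercept patients stop more and 0.12 when placebo patients stop more. Together the mixed rule spans about 0.05–0.08 in the first direction and 0.12–0.17 in the second.

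**6. The window itself.** A final visit at 30 ± 10 days falls on days 20 to 40 after the last dalantercept/placebo dose, so a scan on days 29 to 40 misses a 28-day window counted from that dose. Section 15.4.1 does not name the drug. Section 10.3 refers to the pharmacist "who prepares the study drug (dalantercept or placebo"), which suggests the injection, but axitinib is dosed continuously and could end later. The choice moves only about 1 event per 130 patients.

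**The case against.** **There is one rule, and the parenthesis supplies it.** Largely right. The lead-in confines censoring to patients without an event, and bullet 2 is an express exception. Censoring all stoppers also sits badly with death from any cause as an event and with scheduled follow-up for progression. A reader might infer that the section gives no usable rule. The text does not support that: the mixed rule is the better reading, and bullet 1 only leaves some doubt. But the mixed rule is the asymmetric one.

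**The SAP will settle it.** It may. Section 15.1 defers detail to it, and Section 10.7 places the re-estimation details in the SAP and DMC charter, which suggests they should exist by then. Section 15.6 sets only database lock as the deadline. The effect at the re-estimation is small in any case: 1.3 to 2.6 fewer pooled events if late events are excluded.

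**Type I inflation needs placebo patients to stop more.** Correct. Section 10.6.1 requires discontinuation for certain events related to dalantercept/placebo, so the opposite pattern is at least as plausible, and then the mixed rule is conservative and costs power. A reader might infer that the trial's false-positive rate is inflated. The documents do not support either direction.

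**The two readings give different verdicts.** In simulation they disagreed in 4% to 10% of trials at a common date. A reader might take this as evidence of bias. It is not: window-only had 67.4 to 77.8 events against 82, and two unbiased nested log-rank tests with those counts disagree in 11.5% to 5.3% of trials.

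**Scans during a permitted dose hold.** A reader might infer that these fall outside the window. If dosing resumes, the pre-hold dose is not the last dose, so they do not.

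**Few patients are affected.** Bullets 2 and 3 and the scan exemption do narrow the group. The bias shrinks but remains: with 25% of stoppers scanned, the mixed HR is still 0.675 against 0.650.

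**Conclusion.** The point holds as a defect of the rule, and should be fixed. Section 15.4.1, most naturally read, keeps late events and deletes event-free follow-up over the same period, which overstates the hazard after stopping in the arm that stops more. Under assumed unequal stopping, the mixed rule's one-sided error at nominal 0.10 is about 0.05–0.08 or about 0.12–0.17, depending on which arm stops more. With equal stopping there is no material difference between the rules. In the 10% vs 30% case, the HR moves from about 0.65 to 0.68–0.73.

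All of this rests on assumed stopping rates, accrual, hazard after stopping and scan exemption. The documents fix neither size nor direction, and the SAP, not in the supplied text, may already resolve the rule. Confidence is high in the asymmetry as worded and low in its actual effect.

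**What to change.** In Section 15.4.1 and the SAP, before the sample size re-estimation and the 82-event count:

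1. State one rule in which events and censoring use the same follow-up. The simplest change is to censor event-free patients at their last evaluable scan, on or off treatment, keeping the existing missed-assessment and new-therapy rules. The alternative limits both events and censoring to the on-study window. The choice is an estimand decision for the sponsor.
2. Pre-specify the rule not chosen as a named sensitivity analysis. Section 15.4.1 promises analyses with other PFS definitions but does not name this one.
3. Reword the lead-in and bullet 1 to match, saying explicitly what happens when a patient stops and later progresses or dies.
4. If a window is kept, name the drug whose last dose starts it, and reconcile the 28 days with the final-visit scan at 30 ± 10 days.

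**Cost.** Wording only; no new scans or patients. With all follow-up, off-treatment progression dates are coarser (3-monthly), and patients on new therapy or axitinib alone are exempt from scans, so recovery is partial. Under the assumed scenarios its power was 0.65–0.81 against 0.74–0.81 for window-only when each waits for its own 82 events; at a common date the difference was −0.04 to +0.04. Window-only reaches 82 events 1.0 to 4.7 months later, discards scheduled scans, and leaves censoring at treatment stop possibly informative.
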